5.2 Reporting Procedures for Serious Adverse Events

All AEs will be recorded in participants medical notes on EPIC (electronic healthcare record used in the Cambridge University Hospitals NHS Foundation Trust). If an AE evolves into a condition that meets the regulatory definition of 'serious', it will be reported on the SAE Report Form and submitted to the Sponsor. AEs and SAEs will be collected until the end of the study. If an AE/SAE occur at the last visit, the outcome of these will be followed-up as clinically indicated.

When reporting adverse events, all pertinent data protection legislation must be adhered to.

The serious adverse event report should contain the following information:

- 1. Study identifier
- 2. Participant's unique study number
- 3. Date of birth
- 4. Event description
- 5. Start date of event
- Laboratory tests used and medical interventions used to treat the SAE
- 7. Planned actions relating to the event, including whether the study device was discontinued
- 8. Statement on the patient's current state of health
- 9. Reason for seriousness (i.e. death, life threatening, hospitalisation, disability/incapacity or other)
- 10. Evaluation of causality (including grade of relatedness) with the following (more than one may apply):
- a. the investigational treatment
- b. the clinical study/a study specific procedure
- c. other: e. g. concomitant treatment, underlying disease
- 11. Reporter's name, date and signature

If the above information is incomplete at the time of initial reporting, all appropriate information should be provided as soon as this becomes available.

The relationship between the study medication and SAE should be assessed by the investigator, as should the anticipated or unanticipated nature of any SAEs. All SAEs whether or not deemed related to the study medication and whether anticipated or unanticipated must be reported to the Sponsor by email or fax within 24 hours (one working day) of the Investigator learning of its occurrence.

6. STATISITICS

6.1 The Number of Participants

Since this is a feasibility study, formal sample size calculations are not required at this stage. However, we searched previous reports of the studies using Botnia clamps to obtain a range of standard deviations (SD) of the primary outcome, M-value (defined as average glucose infusion rate when euglycaemic steady state has been reached after the start of insulin infusion, and is expressed in milligrams of glucose per kilogram of body weight per minute).

Considering the statistical power of 80%, α=0.05, desired increase in M-value (improvement in insulin sensitivity) of 15% (assumed pre-treatment and post-treatment means are shown below), SD for M-values of 1.5 mg/kg*min (chosen based on the reported or calculated SD in previous studies with SD ranging from 1.2 to 2.5 mg/kg*min (13, 15-18)) and within-person correlation coefficient of 0.7 (calculated based on the reported data of previous study using Botnia clamp in healthy volunteers (18)), the sample size required is N=10. Accounting for a possible dropout/ technical failure rate with clamps / cannulation etc. of 20%, the target sample size is 12 (i.e. 24 Botnia clamps in total). We will allow for the replacement of up to 5 recruits if they are deemed unable to study (e.g. poor venous access). Analysis will be performed in STATA version 16 (14).

6.2 Sampling

A simple random sample of healthy adult volunteers will be used to maximise the representativeness of this population stratum. We are going to use poster advertisements in the Wolfson Diabetes and Endocrine Clinic. In addition, the study will be advertised through social media.

6.3 Analysis of Endpoints

Continuous variables will be shown as mean and standard deviation (SD) for normally distributed variables or median and interquartile range (IQR) when there is a departure from normality. Primary outcome, M-value, will be shown as mean and standard error of the mean (SEM) for comparability with previous literature. Insulin secretion will be expressed in units per kg of total body weight. First phase insulin response will be calculated as an incremental trapezoidal area under the curve in the first 10 minutes of the intravenous glucose tolerance test component of the Botnia clamp. Categorical variables will be shown as N (%). The study is powered for the primary outcome being M-value (mg/kg*min). Paired t-test will be used to test the differences in M-values between sumatriptan and placebo study days. Logarithmic

transformations will be applied as appropriate to approximate normal distribution. All tests will be two-sided with statistical significance defined as p<0.05. Data will be collected at the screening visit and subsequent 2 visits by the principal investigator and research nurses. The principal investigator will analyse data at the end of the study. Microsoft Excel and STATA (version 16)(14) will be used for analysis.

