2. STUDY DESIGN AND METHODS

The design is a random order double blinded placebo controlled cross-over design of "day case" physiological studies with at least 1 week between studies. A single dose of sumatriptan (100 mg) or placebo allows inpatient dispensing and eliminates the effects of weight loss as a potential confounder. This proof of concept study involves performing detailed physiological studies in overweight adults (aged 18 to 65 years) without other known medical conditions following ingestion of a single dose of sumatriptan or placebo. The study will take place in the Translational Research Facility (TRF) which is embedded in the NIHR/Wellcome Trust Clinical Research Facility affiliated with the Cambridge University Hospital.

All subjects (10 to 12 volunteers) will undergo a screening visit. This will include an assessment of inclusion/exclusion criteria (outlined below), physical exam, alcohol and substance screening test, pregnancy test for women and routine blood tests (full blood count, urea and electrolytes, HbA1C, liver function tests, blood borne viruses).

We have research infrastructure and personal expertise to perform both insulin clamp studies (12) and frequently sampled intravenous glucose tolerance tests (FSivGTT). We have a research pharmacy who can source and repackage sumatriptan / placebo. The assessment of insulin sensitivity and insulin secretion usually requires separate study days. In this study, we aim to combine these into a single 3 hour physiological study combination (FSivGTT followed by a hyperinsulinaemic euglycaemic clamp (HEC) sometimes termed a "Botnia clamp") (13). This markedly reduces the burden on participants and is the most parsimonious way for us to deliver this proof of concept study. We will study participants without diabetes to allow us to assess both insulin secretion and sensitivity. The Botnia clamp technique is described in detail in the Study Procedures and Interventions section. Data will be collected at the screening visit and subsequent 2 visits by the principal investigator and research nurses. The principal investigator will analyse data at the end of the study. Microsoft Excel and STATA version 16 (14) will be used for analysis.

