4.3 Study Assessments/Interventions

All subjects will undergo a screening visit. This will include: assessment of inclusion / exclusion criteria; height and weight measurement (using standard calibrated stadiometers and scales, respectively); physical exam; urine sampling for alcohol and substance screening

test; urine pregnancy test for women, and routine blood tests (full blood count, urea and electrolytes, liver function tests and HbA1C). Eligible subject will proceed to Visit 1 (day 0) between 1 to 28 days after the screening visit and Visit 2 (day 7 to 31 after visit 1) at which they will receive a single dose sumatriptan (100mg) or placebo in a random order and Botnia clamp studies (described in detail below) will be performed.

We have research infrastructure and personal expertise to perform these physiological studies (12). In this study, we aim to combine FSivGTT and hyperinsulinaemic euglycaemic clamp (HEC) into a single 3 hour physiological study combination (FSivGTT followed by a HEC sometimes termed a "Botnia clamp") (13). This technique has been reported to have a high reproducibility and validity compared to traditional HECs in non-diabetic individuals with and without family history of T2D (13). The assessment of insulin secretion and sensitivity typically takes place on separate days. Combining them in a single 3h study substantially reduces the burden on participants and is the most parsimonious way for us to deliver this proof of concept study as alluded to earlier. We will study participants without diabetes to allow us to assess simultaneously both insulin secretion and sensitivity.

Botnia clamp technique

The procedure will be undertaken in the morning following an overnight fast of at least 10h. Participants will remain rested on a bed during the procedures. It lasts 3h and consists of two components: 1) FSivGTT (60 min) followed by a 2) HEC for the remaining 120 min.

1) FSivGTT

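### The primary paired t-test has no period term in a two-period crossover; a visit effect would cost power if the sequences are equal and shift the estimate if they are not

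*Protocol*

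**What the plan says.** The Study Design and Methods section describes a "random order double blinded placebo controlled cross-over design" with at least one week between the two study days. Section 4.3 places the second visit 7 to 31 days after the first.

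For the primary outcome, section 6.3 states: "Paired t-test will be used to test the differences in M-values between sumatriptan and placebo study days". It adds: "All tests will be two-sided with statistical significance defined as p<0.05". Appendix 3 sizes the trial on the same paired test. Neither place mentions a term for period or sequence.

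On presentation, section 6.3 says: "Primary outcome, M-value, will be shown as mean and standard error of the mean (SEM) for comparability with previous literature". It does not mention an estimate of the sumatriptan-placebo difference or an interval for it.

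The protocol states no sequence ratio. Section 6.1 allows for 20% loss and adds: "We will allow for the replacement of up to 5 recruits if they are deemed unable to study". It does not say which sequence a replacement receives.

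**The concern.** In a two-period crossover, each participant's sumatriptan-minus-placebo difference contains any systematic difference between visits. It enters with a plus sign in one sequence and a minus sign in the other. Randomising the order makes it possible to separate this from the treatment effect, but a paired t-test on the pooled differences does not do so.

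There are two consequences:

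- With equal sequences, the visit effect cancels in the mean but stays in the spread of the differences. The test becomes conservative and loses power.
- With unequal sequences, part of it also remains in the mean, so the estimate for that trial is off target.

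The margin is thin: the planned power is about 83% at n = 10, and this test answers the trial's main question.

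**Working it through.** **Inputs from Appendix 3.** Means 8.0 and 9.2 mg/kg/min (difference 1.2), SD 1.5 on each day, within-person correlation 0.7, two-sided α = 0.05, power 80%.

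**The plan's own figure.** The variance of the paired difference is 2 × 1.5² × (1 − 0.7) = 1.35, so its SD is 1.162. From the noncentral t with n − 1 degrees of freedom, power is 77.4% at n = 9 and 82.7% at n = 10. The stated n = 10 is reproduced.

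**The same calculation with a period term.** For equal sequences the standard error is unchanged and the degrees of freedom are n − 2. Power is 75.7% at n = 9, 81.5% at n = 10 and 89.6% at n = 12. The required number stays at 10.

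**Adding a visit effect.** Let π be the visit 1 minus visit 2 difference. *Assumption:* π lies between 0 and 0.8 in size; 0.8 is 10% of the assumed mean of 8. The expected difference is 1.2 + π for those who take sumatriptan first (n1) and 1.2 − π for those who take placebo first (n2).

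*Equal sequences.* The bias is zero. The variance seen by the paired test becomes 1.35 + π² × n/(n − 1). At 5:5:

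- π = 0.4: 1.35 + 0.16 × 10/9 = 1.528, SE = √(1.528/10) = 0.391
- π = 0.8: 1.35 + 0.64 × 10/9 = 2.061, SE = √(2.061/10) = 0.454
- π = 0: SE = 1.162/√10 = 0.367

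Simulation (200,000 trials per cell) at 5:5:

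| π | Paired power | Adjusted power | Paired type I error |
|---|---|---|---|
| 0 | 83% | about 81.5% | 5% |
| 0.4 | 79% | about 81.5% | 3.9% |
| 0.8 | 68% | about 81.5% | 1.9% |

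*Unequal sequences.* The bias is π × (n1 − n2)/n. For π = ±0.8:

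- 6:4: ±0.8 × 2/10 = ±0.16, or 13% of 1.2
- 8:4: ±0.8 × 4/12 = ±0.27, or 22% of 1.2

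Power then depends on the direction of the shift. At 6:4 the paired test has 54% if the shift is adverse and 80% if it is favourable, against 80% adjusted. At 8:4 it has 56% or 94%, against 86% adjusted. The highest type I error among the splits examined was about 6.5%, at 7:3.

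**Cost of adjusting when π = 0.** The adjusted SE is 1.162 × √(1/n1 + 1/n2)/2. Power moves as follows:

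- 5:5: 82.7% to 81.5% (about 1 point)
- 6:4: 82.7% to 79.9% (3 points)
- 8:4: 90.2% to 85.9% (4 points)
- 7:3: 82.8% to 74.7% (8 points)

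**Presentation.** At n = 10 the SEM of one day's M-value is 1.5/√10 = 0.474. Combining two of these as if independent gives 0.474 × √2 = 0.671. The SE of the paired difference is 0.367. A reader who had only the two SEMs would therefore overstate the SE by a factor of 0.671/0.367 = 1.83.

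**The case against.** The strongest objection is that the protocol gives no evidence of a visit effect. Section 4.3 reports good reproducibility for the technique, the team is experienced, and a visit difference of 0.8 is at the top of the assumed range. At 0.4 the gap between the two tests at 5:5 is only about 2 points. This stands: the harm is conditional, and its size is not known from the documents.

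A reader might infer that the planned test is invalid, or that it dilutes the treatment effect. The documents do not support that. With equal sequences there is neither bias nor attenuation, only a larger SE. Bias belongs to a trial whose completed sequences are unequal, and it can go either way. Averaged over simple randomisation, the paired test is unbiased and its type I error is 5.1% even with a visit effect of 0.8.

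A reader might also infer that serious imbalance is likely. Unrestricted randomisation of 12 would give 8:4 or worse with probability 39%, but the protocol says only that the order is random. The method may be set out elsewhere, and nothing suggests that replacement depends on sequence.

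Finally, the SEM is a descriptive choice with a stated reason, and it does not enter the test. The factor of 1.83 arises only if the two SEMs are wrongly treated as independent. This supports the main point and is not a separate fault.

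What remains is that the test itself is fixed in section 6.3, and a better one is available on the same data.

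**Conclusion.** The point holds as a recommended improvement. The protocol names, and sizes the trial on, a paired t-test that leaves out the period in a two-period randomised-order crossover.

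For an assumed visit difference of 0 to 0.8 mg/kg/min, the paired test at 5:5 ranges from about 1 point better than the adjusted test to about 14 points worse (81.5% against 68%). With unequal completed sequences, a visit difference of 0.8 shifts the estimate by up to ±0.16 at 6:4 and ±0.27 at 8:4. These figures rest on the Appendix 3 inputs, on no carry-over, and on a visit effect that the documents neither report nor rule out.

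**What to change.** In section 6.3, replace the paired t-test with a linear model for M-value with participant, period and treatment. An equivalent is the two-sample t-test comparing period differences between the two sequences. Report the sumatriptan-placebo difference with its 95% CI as the primary result; the planned mean and SEM can stay beside it for comparison with the literature. Make the matching change to the test named in Appendix 3.

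State that the two sequences are kept balanced, and that a replacement takes the sequence of the person replaced. This matters because the power cost of adjusting, if there is no visit effect, grows with imbalance.

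The change takes a few sentences and no extra participants or clamps. With balanced sequences it costs one degree of freedom, and n = 10 remains sufficient.

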7. ETHICAL AND REGULATORY COMPLIANCE

The study will be carried out in accordance with Good Clinical Practice and the Declaration of Helsinki. The participants may not have direct short-term benefits from taking part in the study which is explained in the PIS. However, the results of this study will help design future studies focused on people with diabetes and open new research avenues and ultimately clinical benefits of adjunct treatment to insulin (T1D) and/or another medication in the treatment of T2D. The risks are described in detail in the PIS and can be broadly classified into procedure related risks (PIS) and side effects of sumatriptan (Appendix 4; PIS). Participants will keep a copy of the PIS and ICF while another copy will be kept in the Investigator Site File and the participants medical records. Strategies taken to minimise these risks are also described in the PIS and the Background section of this Protocol. The study will be conducted on overweight otherwise healthy volunteers as this is the first study in humans investigating the effects of sumatriptan on glucose homeostasis independent of weight loss and allows an assessment of insulin secretion and sensitivity. We have chosen the most parsimonious design and method to minimise the burden to participants. Data collection methods involve measurement of vital and anthropometric parameters as well as frequent blood sampling, and participant dignity will always be maintained throughout the study.

7.1 Data Protection and Patient Confidentiality

All data will be processed in accordance with the General Data Protection Regulation (GDPR). Electronic data will be stored on password-protected computers. All paper records will be kept in locked filing cabinets, in a secure office. Only members of the research team will have password access to the anonymised electronic data. Only members of the research team will have access to the filing cabinet. Paper copies of the data will be stored for 5 years in line with the Data Protection Act 2018. The investigators and the rest of the study team will ensure that personal information of the participants is always protected. In the correspondence with the Sponsor confidentiality and anonymous nature of the data will be preserved by using unique participant identifiers (study numbers) instead of the names.

All samples will be labelled using a unique study ID which is not identifiable outside the clinical study team. Residual blood samples will be stored for potential future analysis in ethically approved studies for up to 5 years.

Participants will be able to send questions, comments and requests about their personal data to [name] (Data Protection Officer at Cambridge University Hospitals) at [contact].

7.2 Indemnity

The clinical investigators are indemnified to cover negligent harm to patients participating in the study by their membership of medical defence organisations.

The Sponsor (Cambridge University Hospitals NHS Foundation Trust) has insurance to cover the costs of illness or injuries arising from the design, management and conduct of the study. The Sponsor has made no arrangements for payment of compensation in the event of harm

to the research participants where no legal liability arises.

8. DISSEMINATION POLICY

The Sponsor (Cambridge University Hospitals NHS Foundation Trust) owns the data arising from this study. Upon completion of the study, the data will be analysed and tabulated and the Final Study Report will be prepared. The Final Study Report will be kept together with other study documents and a copy will be sent to the Funder (DRWF) as specified in the Terms and Conditions of the award and to the Research and Development Office of the Sponsor. The DRWF will be acknowledged in the publications arising from this project but have no review or publication rights *per se*.

Data will be published in internationally peer-reviewed scientific journals. The investigators ([name] and [name]) and other members of the study team will be co-authors. The privacy of each subject and confidentiality of their information shall be preserved in reports and publication of data. There are no time limits to publish the data but the investigators will endeavour to submit the first scientific report as soon as possible after the analysis is completed.

The participants will be notified of the outcome of the study in a form of a lay summary of the results and their meaning for future research and people with diabetes after the first scientific report has been published. The participants are welcome to request the detailed report directly from the PI.

The study protocol and full study report will be part of the publications and therefore available publicly. Direct access to the individual level source data will be provided for audits, Ethics

Committee review and regulatory authority inspections during and after the study. The fully anonymised data may be shared with third parties for the purposes of advancing management and treatment of diabetes. Appropriate procedures agreed by the investigators will be put in place for data review, database cleaning and issuing and resolving data queries.

9. APPENDICES

Appendix 1 Schedule of Procedures

	When?		
	Screening visit	Visit 1	Visit 2
What happens?			
Eligibility review	x	x	x
Informed consent	x		
Medical history	x		
Physical examination	x		
Weight measurement	х	x	х
Height measurement	x		
Vital signs	x	x	х
Adverse event review		x	х
Concomitant medication review	х	x	х
Fasted (10 hours)		x	х
Blood sample collection	x		
Pregnancy test (women only; urine sample)	х	x	x
Substance abuse screen (urine sample)	х	x	x
Study drug administration		x	x
Botnia clamp study		x	x

Appendix 2 Study timeline

[figure not shown]

Figure 1 Project timeline

NB Periods of intensive research activity are timed with an academic/research block of the principal investigator which is part of combined clinical and academic training in diabetes and endocrinology. We are aware that the start of the study may be affected by the state of the COVID19 epidemic.

Schedule of events is presented in Appendix 1.

Appendix 3 Details of power calculation

The following is a power calculation for the cross-over trial described in this proposal comparing the effects of a single dose of sumatriptan vs placebo on insulin sensitivity expressed as M-value (mg/kg*min) using paired samples t-test.

 α =0.05 and power 80% were set conventionally.

Assumed pre-treatment mean for M-value: 8.0 mg/(kg*min)

Assumed post-treatment mean for M-value: 9.2 mg/(kg*min), i.e. 15% improvement in insulin sensitivity

r=0.7- calculated within-person correlation coefficient

SD=1.5 mg/(kg*min)- assumed standard deviation for pre-treatment and post-treatment M-value

The above parameters yield n=10 for the paired samples t-test.

Accounting for 20% attrition the target n is n=10/0.8=12

Further details:

1) Within-person correlation

Pre-treatment mean for M-value of 8 mg/(kg*min) was chosen based on the reported estimate in Wilms *et al.* using Botnia clamps in healthy volunteers: this was the estimate for the control group (18). The desired improvement in insulin sensitivity is 15% and therefore, the assumed mean for post-treatment M-value is 9.2 mg/(kg*min).

The r (within-person correlation coefficient) was calculated from the reported estimates of SE (and calculated SD) for M-value and n in the study by Wilms *et al.* (18). The following formula was used (19):

Corr=
$$(SD_F^2 + SD_C^2 - SD_{diff}^2)/(2*SD_F*SD_C)$$

Inserting the calculated SD from the reported estimates in the formula above yields r=0.7.

2) Assumed standard deviation for pre- and post-treatment mean M-value

Several previous studies reported SE or SD for M-value. When only SE was available SD was calculated as SD=SE * n^{1/2}. The reported or calculated SD in previous studies ranged from 1.2 to 2.5 mg/kg*min (13, 15-18). We arbitrarily chose SD=1.5mg/kg*min for pretreatment and post-treatment M-value to represent a biologically plausible SD in this study and used it in the calculation of the target n for paired samples t-test.

